Within the SMART, a measure of initial response is assessed following implementation of the primary outreach approaches in order to evaluate each site's need for further adaptation. In this way, testing is tailored to meet the needs of communities and their Latinx individuals and families by providing enhanced testing strategies to slow-responding sites. This measure of initial response is referred to as a primary tailoring variable. In the proposed study, the primary tailoring variable is whether a site is operating at a threshold of 80% testing capacity, based on the frequency and per capita testing rates and presumption of 50 tests per testing event. The AIS each represent distinct plans of testing outreach approaches. Within the SMART, it is then possible to evaluate which adaptive sequence is the most effective in impacting Latinx testing rates and secondary outcomes such as health maintenance behaviors.

Specifically, the proposed RADx SMART includes 4 embedded adaptive intervention strategies (AIS). Sites and individuals in the proposed Latinx sampling frame will receive one of two first-stage implementation outreach strategies: Basic Outreach approaches or Basic Outreach plus Promotoras Comunitarias. Primary outcomes will be site level testing rates and individual level COVID-19-related health behaviors. After the initial 4 weeks (2 testing events), sites will be re-randomized in the second-stage randomization to either stay the course stationary events or to a mobilization intervention. Thus, for the primary criterion outcome of testing capacity, the SMART design includes 4 embedded site level adaptive intervention strategies (AIS): (1) starting with culturally adapted Basic Outreach, and staying the course; (2) starting with Basic Outreach followed by mobilization intervention; (3) starting with Basic Outreach plus Promotoras Comunitarias and staying the course; and (4) starting with Basic Outreach plus Promotoras Comunitarias plus mobilization intervention. In addition, as a booster to the Promotoras Comunitarias intervention, for health behavior outcomes, individuals tested at Basic Outreach sites will receive pamphlet health promotion pamphlets, and those tested at Promotoras Comunitarias sites, will receive a health pamphlet plus a Promotoras de Salud intervention.

[figure not shown]

Figure 4.3.1

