#### 4.3.b Embedded AIS Research Questions and Aims

The specific research questions and aims are the following. Question 1a: Is Basic Outreach plus Promotoras Comunitarias more effective for maximizing testing capacity than Basic Outreach? Question 1b: For individuals tested, is Pamphlet plus Promotoras de Salud more effective than Pamphlet only in supporting positive health behaviors for individuals tested? [(A+B+C+D) vs (E+F+G+H)]. Research Aim Question 2: Among slow responding sites, does the mobilization intervention yield an increase in individual positive health behaviors and in site testing capacity? [(D+H) vs (C+G)].

Each of these AIS research questions is depicted in Figures 4.3.2 through 4.3.3:

**Question 1a:** Is Basic Outreach plus Promotoras Comunitarias more effective for testing capacity than Basic Outreach alone, for Latinx communities?

**Question 1b:** For individuals tested, is Pamphlet plus Promotoras de Salud more effective than Pamphlet only in supporting positive health behaviors for individuals tested, and increasing site testing rates?

**Aim 1a:** Is Basic Outreach plus Promotoras Comunitarias more effective for testing capacity than Basic Outreach alone?

**Aim 1b:** For individuals tested, is Pamphlet plus Promotoras de Salud more effective than Pamphlet only in supporting positive health behaviors for individuals tested, and increasing testing rates?

[figure not shown]

Figure 4.3.2

**Research Aim Question 2:** Among slow responding sites, does the mobilization intervention yield an increase in site testing capacity?

**Aim 2:** Among slow responding sites, does the mobilization intervention yield increase in site testing capacity?

[figure not shown]

Figure 4.3.3

In addition to research questions 1 and 2, the SMART design also allows for an omnibus comparison; after starting with Basic Outreach or Basic Outreach + Promotoras Comunitarias, we can examine which of the embedded adaptive intervention strategies is more effective overall for testing capacity and health behavior maintenance [A vs B vs C vs D vs E vs F vs G vs H]. Although not a specific aim of the proposed study, agencies and stakeholders may be particularly interested in this question and our study design will allow us to test this, focusing on the combined R1 and R2 strategies.

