#### 4.3.f Power

Power for detecting the optimal AIS was estimated using the SMARTAR package 1.0.0 in R R^71. We chose a power convention of .80 with a two-sided alpha level of .05 to reduce the probability of obtaining a false positive (Type-I error). For research question 1, balanced response rates of 50% of sites having adequate response and 50% slow responding, 36 sites for a continuous outcome (e.g., rates) can minimally detect a small difference of .27 among the combined group comparisons [(A+B+C+D) vs (E+F+G+H)], and power to minimally detect a medium effect of .54 (n=18 sites) [(D+H) vs (C+G)]. For the global test of the optimal treatment strategy (n=36 sites), the study is powered to minimally detect an effect of .40, a moderate effect. Power for detecting the optimal AIS was estimated using the SMARTAR package 1.0.0 in R^71.

We must also consider response scenarios that include either more slow-responding or even less slow responding sites before the tailoring intervention (i.e., 80% of the randomly allocated sites responded at capacity and 20% were below threshold; or alternatively, only 20% responded and 80% were below capacity initially). In each of these "unbalanced" response scenarios, power for research question 1 is the same as the balanced design above. Although we do not anticipate such a large range of slow responding sites based on our preliminary testing; for the slow-responding sites only, a bracket range of 80/20 response ratio (resulting in 8 slow responding sites [(D+H) vs (C+G)]) to a high of 20/80 ratio (resulting in 28 slow responding sites [(D+H) vs (C+G)]). In these scenarios, for research question 2, the study is powered .80 to minimally detect a difference of 1.3 (a large effect) or to minimally detect a moderate effect of .35 (a moderate effect), respectively, for 8 to 28 total slow responding sites for research question 2.

[figure not shown]

Figure 4.3.f Power Curve.

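### The omnibus contrast in SAP 4.3.b is written over eight cells split by early response, which contradicts the four strategies of 4.3.a and the A1, A2, A1A2 model of 4.3.d

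*SAP*

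**What the plan says.** - **The omnibus question (SAP 4.3.b).** The plan asks which embedded strategy does best and puts the contrast in brackets, as follows: "more effective overall for testing capacity and health behavior maintenance [A vs B vs C vs D vs E vs F vs G vs H".
- **Its status and focus (SAP 4.3.b).** The next sentence begins "Although not a specific aim of the proposed study", notes that agencies and stakeholders may want the answer, and ends "focusing on the combined R1 and R2 strategies".
- **Number of strategies (SAP 4.3.a).** Four are listed: basic outreach with or without promotoras, each followed by staying the course or by mobilization.
- **Response (SAP 4.3.a).** "the primary tailoring variable is whether a site is operating at a threshold of 80% testing capacity". Re-randomization follows the first 4 weeks (2 testing events). Testing capacity is also named as the primary criterion outcome.
- **Model (SAP 4.3.d).** The equation for the optimal strategy contains A1, A2, A1A2 and a pre-test covariate. It has no response term.
- **Meaning of the letters (SAP 4.3.d and 4.3.f).** A to D and E to H are the two first-stage arms. The slow-site question is (D+H) against (C+G), and its size is the full count of slow sites: 18 in the balanced scenario, 28 in one unbalanced scenario, and in the other "resulting in 8 slow responding sites [(D+H) vs (C+G".
- **Power (SAP 4.3.f).** "For the global test of the optimal treatment strategy (n=36 sites), the study is powered to minimally detect an effect of .40". The effect metric and the degrees of freedom are not given.

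**The concern.** If C, D, G and H hold every slow site, the other four letters hold every site that reached the threshold. An eight-cell test then sets responding sites against slow sites. Response is observed after the first randomization and is measured on the same construct as the outcome. Sites that did well early may do well later whatever they were assigned, and that alone can produce a significant result.

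The test also cannot rank strategies. Each strategy takes in both responding and slow sites, so a strategy is a pair of cells. The cell with the highest mean will usually be a responding cell, and no agency can assign a site to be a responder. A statistician who followed the bracket could report that strategies differ when only early performance does.

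**Working it through.** **1. The plan's own figure.** The global .40 was tried as Cohen's f in a one-way F test with N = 36, k groups, noncentrality 36f² and two-sided alpha .05.
- 80% power needs f = .585 for k = 4 and f = .71 for k = 8.
- At f = .40 the power is 45% (k = 4) and 29% (k = 8).
- A pre-post correlation r would reconcile the figure if √(1 − r²) = .40/f. This gives r = √(1 − (.40/.585)²) = .73 for four groups and √(1 − (.40/.712)²) = .83 for eight.

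The figure was not reproduced. The metric is undefined and the named R package was not available, so this does not show that .40 is wrong. It shows that .40 is not tied to a test.

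**2. Two tests side by side.** The bracket has 8 cells, so 8 − 1 = 7 df. The 4.3.d equation gives 2 × 2 = 4 strategy means, so 3 df for A1, A2 and A1A2. It cannot produce eight cell means.

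**3. Size of the problem, by hand.** Assume no effect of A1 or A2, half the sites slow, and a normal early level that correlates ρ with the later outcome (ρ is an assumption; the documents give none). A median split on the early level explains a share 2ρ²/π of outcome variance. For ρ = .5:
- share = 2 × .25/3.1416 = .159
- f² = .159/(1 − .159) = .189
- noncentrality = 36 × .189 = 6.8
- rejection on 7 and 28 df: about 34%, instead of 5%

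**4. Simulation.** 36 sites, 18 per first-stage arm, all re-randomized 1:1 within arm and response status, no intervention effect, no covariate, half the sites expected to be slow, 3,000 runs per setting:

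| ρ | Eight cells (7 df) | Four strategies (3 df) |
|---|---|---|
| 0 | 5% | 5% |
| .2 | 7% | 5% |
| .3 | 12% | 4% |
| .5 | 32-34% (two runs) | 4% |
| .7 | 73% | 2-3% |

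With 20% or 80% of sites responding, the eight-cell test rejects at about 10%, 23% and 50-53% for ρ = .3, .5 and .7.

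**5. With a pre-test covariate, as 4.3.d specifies.** The first column is the assumed correlation of the pre-test with both the early level and the outcome:

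| Pre-test correlation | ρ | Eight cells |
|---|---|---|
| .3 | .5 | 24% |
| .5 | .5 | 13% |
| .5 | .7 | 42-44% (two runs) |
| .7 | .7 | 16% |

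**6. Where the excess comes from.** When response status is added to the model, the test among the cells returns to about 4-5%. The excess is therefore the gap between responding and slow sites. Among false rejections at 50% response without a covariate, the top cell was a responding cell in 93% of cases at ρ = .3, and in 98% or more at ρ of .5 and above.

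**7. Does the plan expect such a gap?** SAP 4.3.f lowers the projected individual tests from about 3600 to 2520 because half the sites are slow. At 3600/36 = 100 per site, 2520 = 18 × 100 + 18 × 40. That split is inferred, but it suggests the plan expects slow sites to stay behind.

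**The case against.** The strongest reply is that the bracket is loose notation and the real analysis is sound. The sentence around it asks about strategies, and the next one says "focusing on the combined R1 and R2 strategies". Section 4.3.d gives a four-strategy equation, and 4.3.f refers back to that equation for comparing strategies and mentions comparisons among the four. No analysis text describes a 7-df test. This largely stands: the defect is a contradiction between bracket and model, and the model holds its error rate. It does not remove the point, because the bracket is the only contrast written out for the omnibus question and the plan never says that the model overrides it.

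The disclaimer "Although not a specific aim of the proposed study" also stands and limits the consequences. Against it, 4.3.a promises to identify an optimal strategy and 4.3.f claims power for a global test, so the result is likely to be used.

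A reader might infer four stronger things that the documents do not support:
- *The bracket is the only overall test.* Sections 4.3.d and 4.3.f point to another.
- *Any persistence of site performance makes the test significant.* At ρ = .2 it rejects at about 7%, and the pre-test covariate lowers the rate further.
- *The main questions are compromised.* Questions 1a and 1b compare first-stage arms, and Question 2 compares second-stage options within slow sites. None sets responding sites against slow ones.
- *The global power figure is shown to be wrong.* Its metric is undefined.

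Figure 4.3.1 and Table 4.3.1 are not in the text available here, so what separates A from B, or E from F, cannot be confirmed.

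**Conclusion.** Wrong as written, with limited reach. Followed literally, the eight-cell bracket tests early response along with treatment and does not compare the four strategies. For testing capacity with 18 of 36 sites slow and no intervention effect, its false rejection rate is about 7% to 73% for assumed correlations of .2 to .7 without a covariate, and about 13% to 44% in the covariate settings tried. The four-strategy test stays at about 2-5%.

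This rests on three assumptions: the early-to-late correlation, the inference that A, B, E and F are the responding sites, and re-randomization of all sites balanced on response. Health behaviors do not define response, so inflation there may be slight.

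**What to change.** - **SAP 4.3.b:** replace the eight-cell bracket with the joint 3-df test of A1, A2 and A1A2 from the 4.3.d equation, on all 36 sites. Pool responding and slow cells within each A1 × A2 combination, with letters taken from Figure 4.3.1.
- **SAP 4.3.b:** state that cells are not compared across response status.
- **SAP 4.3.f:** state that the global .40 refers to this 3-df test, and give its effect metric and any assumed pre-post correlation.

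The cost is SAP wording only. No site, data collection or budget changes, and the model is already in the plan.

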#### **4.3.c Recruitment of 36 Communities in 6 Counties into the Testing Program**

This testing program will build on existing partnerships with 6 county public health authorities in Oregon (see letters of support), that are either designated as a rural county by the Office of Management and Budget (Lincoln, Douglas, Josephine) or have a significant rural population (Lane, Marion, Benton). We will establish contracts with each county to provide them with staffing resources to support additional testing in Latinx communities. In addition, we will work with each county public health agency to develop a County Collaborative that includes key community stakeholders in the Latinx community, including those representing Latinx serving organizations such as non-profits and churches. The focus of the County Collaboratives is to engage the implementation process described in the implementation strategy. Leveraging the county collaboratives' knowledge of county communities, 6 communities (identified by zip code or zip code cluster) within each county will be selected for site implementation. Given that proximity is a critical component for reducing barriers to access in rural communities, and given the composition of the 6 counties, most of the 36 communities who participate in the testing program will be rural. We will employ *a priori* stratification by county and rurality to balance potential confounders, to reflect the hierarchical structure of the design in the analytic plan. Specifically, for the first randomization, within each county, 3 communities will be randomized to the treatment condition and 3 to the control condition (total of 18 per condition, 36 total).

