#### **4.3.d Data Analysis for Aims 1 and 2**

For the primary evaluation aims for determining the optimal strategy for testing Latinx communities and the four adaptive intervention strategies, we will employ standard normal theory generalized linear modeling analysis of covariance fractional factorial analyses using pre-post assessment scores for site and individual level outcomes. Research Question 1 will focus on the combined effects of A1 randomization groups [(A+B+C+D) vs (E+F+G+H)]. Research Question 2 will focus on which A2 strategy works best for slow-responding sites [(D+H) vs (C+G)]. To address the non-independence of subjects in the embedded adaptive intervention designs and crossed factors, we will estimate linear mixed models with weighted least squares using the design effects coding shown in Table 4.3.1.

The general equation to estimate the optimal strategy is given by

$$E[Y|A_1, A_2, O_1] = \beta_0 + \beta_1 A_1 + \beta_2 A_2 + \beta_3 A_1 A_2 + \gamma^T O_1$$

where  $E$  is the expected value of the outcome,  $A_1$  is the initial treatment randomization,  $A_2$  is the second stage treatment randomization and  $\gamma^T$  are the estimates for covariate  $O_1$ , the pre-test covariate. For binary and count data we will employ generalized linear modeling and logit, probit, and poisson link functions for criterion outcomes such as frequency of tests, re-tests, and discrete event behaviors.

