Finally, when considering power for individual level data, a mixed model with two levels (individuals nested within sites) we must consider full capacity scenarios where implementation is realized at full capacity (roughly 3600 tests) to scenarios that obtain a smaller number of individual tests based on response patterns by site. In this case, that is the balanced scenario shown in Figure 4.3.1 given half of the sites are slow responding. That scenario projects a maximum of 2520 level-1 testing units sampled from 36 sites and achieves .80 power to detect a difference of .22 (a small effect) among the group conditions for randomization 1 conditions A1, randomization 2 conditions A2, and their crossed A1A2 interaction, and an intraclass correlation of .05 for the test of comparative intervention strategies from the primary equation shown above. Thus, the study is adequately powered for all multilevel data scenarios for minimum response to maximum response to detect small effect sizes. Power for individual comparisons among the 4 embedded AISs is shown in Figure 4.3.f.

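### The first randomization is stratified by county, but the Question 1 model states no county term; leaving county out makes the A1 test conservative to the extent that county differences remain after pre-test adjustment

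*SAP*

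**What the plan says.** SAP section 4.3.c describes "stratification by county and rurality to balance potential confounders, to reflect the hierarchical structure of the design in the analytic plan". The only concrete allocation rule is by county: "for the first randomization, within each county, 3 communities will be randomized to the treatment condition and 3 to the control condition", giving 18 sites per arm.

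Section 4.3.d proposes "standard normal theory generalized linear modeling analysis of covariance fractional factorial analyses" on pre-post scores at site and individual level, and adds, to deal with dependence between subjects, that "we will estimate linear mixed models with weighted least squares". Its equation contains A1, A2, A1A2 and O1, and O1 is defined as "the pre-test covariate". Neither county nor rurality is named. The individual-level power paragraph in 4.3.f assumes "a mixed model with two levels (individuals nested within sites", with no county level. Protocol section D repeats the analysis-of-covariance sentence without mentioning strata.

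The site-level power statement in 4.3.f treats site rates as continuous, so a normal-theory comparison of 36 sites is a main analysis for Question 1.

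**The concern.** When allocation is balanced within county, county differences cancel out of the treatment contrast. An analysis that ignores county still counts those differences as residual noise. The reported standard error then exceeds the true one, the interval is too wide, and some of the precision gained by stratifying is lost. With only 36 sites this can matter. The plan says that its analysis will reflect the design's hierarchy but does not say how, so whether county is in the model stays open until analysis. Two analysts following this SAP could report different intervals and p-values for Question 1.

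**Working it through.** **Inputs from the SAP.** Six counties with six communities each, 3:3 within county (4.3.c). Two-sided alpha .05, power .80, 36 sites, stated detectable difference .27; at individual level 2520 people, 36 sites, intraclass correlation .05, stated difference .22 (4.3.f).

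**Assumed.** The share *s* of site-level residual variance that lies between counties after pre-test adjustment. The documents give no figure, so a range is shown.

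**The plan's own figures.** With 18 against 18 sites and SD 1, the detectable difference is (1.960 + 0.842) × √(2/18) = 0.934 SD, not .27. Power at .27 is about 0.12. Reaching .27 through the pre-test alone would need a correlation of √(1 − (0.27/0.934)²) = 0.957, which is not stated. At individual level the design effect is 1 + 69 × .05 = 4.45 and the difference is 2.802 × √(4 × 4.45/2520) = 0.235, against .22. These are separate matters and nothing below depends on them. The shifts below are measured from a baseline near 0.95 SD, not from .27.

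**Direction.** Set the residual site variance to 1.

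- True variance of the A1 difference, county effects cancelling: (1 − s) × 2/18 = (1 − s)/9.
- Expected residual mean square without county, 34 df: [29(1 − s) + 5(1 − s + 6s)]/34 = 1 − 4s/34.
- Ratio of model variance to true variance: (1 − 4s/34)/(1 − s) = 1.05, 1.10, 1.22 and 1.38 at s = 5%, 10%, 20% and 30%.
- Detectable difference with five county indicators, 29 df: about (2.045 + 0.854) × √((1 − s)/9) = 0.966 × √(1 − s).

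**Size, site level, A1 only** (400,000 simulated null trials per share; differences in residual-SD units). The last column is power with county at the difference that has 80% power without it.

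| County share | Type I error, no county | Type I error, fixed county | Detectable difference, no county | Detectable difference, fixed county | Power with county |
|---|---|---|---|---|---|
| 0% | 5.0% | 5.0% | 0.962 | 0.966 | 79.7% |
| 5% | 4.5% | 5.0% | 0.952 | 0.941 | 80.9% |
| 10% | 4.0% | 5.0% | 0.944 | 0.916 | 82.3% |
| 20% | 3.2% | 5.0% | 0.924 | 0.864 | 85.1% |
| 30% | 2.5% | 5.0% | 0.905 | 0.808 | 88.1% |

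**All printed terms** (A1, A2, A1A2, O1; A2 assumed 9:9 within arm and unstratified, O1 independent of the residual). Type I error without county is 4.5%, 4.0%, 3.3% and 2.5% at shares of 5% to 30%. Adding county moves the detectable difference from 0.971 to 0.964, 0.962 to 0.939, 0.943 to 0.885 and 0.928 to 0.829.

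**A pre-test that tracks county** (correlation .95 with the county part and .5 within county; total-SD units). At a 10% total county share the difference moves from 0.815 to 0.814, a loss of under 1 power point. At 30% it moves from 0.739 to 0.718, and power from .804 to .826, about 2 points.

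**Individual level** (70 per site, A1 only; share of between-site variance; individual-SD units). The difference moves from 0.240 to 0.239, 0.239 to 0.234, 0.236 to 0.224 and 0.232 to 0.213 at shares of 5%, 10%, 20% and 30%.

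**Limit of the argument.** Section 4.3.d also offers "poisson link functions for criterion outcomes such as frequency of tests". With an assumed mean of 100 tests per site, county log-SD .15 and within-county site log-SD of .1 to .3, a Poisson model without a dispersion term rejected a true null in 17% to 56% of trials, the same with and without county. With a dispersion term, the rate was 1.2% to 3.4% without county and about 5% with it.

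**The case against.** The best reply is that this is under-specification, not error. The formula is introduced as a general one and its covariate term is in vector form. A random county intercept would not appear in a mean equation, and the two levels come from a power calculation. Table 4.3.1 cannot be seen, although it is cited only for effect coding. This stands in part: the SAP does not exclude county. But it does not state it either, and the text defines O1 as the pre-test score alone.

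A second reply is that the harm is in the safe direction and may be small. That also stands. At a 5% share the loss is about 1 point, and the larger losses need 20% to 30% of variance to remain between counties after adjustment, which the documents do not show. They do make county differences plausible: 4.3.c treats county and rurality as possible confounders and mixes designated rural counties with others, and protocol section C says usual outreach is run by county public health and community organizations, whose materials may differ.

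A reader might also infer a gain from adding rurality. The documents do not support one. Section 4.3.c does not say how rurality was balanced within a county or how many rural communities each has, and exact balance under 3:3 needs an even number of them.

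**Conclusion.** The point holds, and the plan should be changed, though the validity of the trial does not turn on it. For A1 in the normal-theory and linear mixed analyses, a model without county is conservative to the extent that county differences survive pre-test adjustment. The loss is about 1 to 8 power points over assumed residual shares of 5% to 30%, and about 2 points or less if the pre-test tracks county closely and the total county share is 30% or below.

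Three stronger readings do not hold:

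- **That false positives rise or the estimate is biased.** In these analyses type I error falls below 5%, and balanced allocation removes county from the contrast.
- **That the same applies to Question 2.** Section 4.3.a states no stratification for the second randomization.
- **That county terms would repair every outcome model.** They do not by themselves correct a Poisson model fitted without a dispersion term.

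**What to change.** In 4.3.d, state that the normal-theory and linear mixed Question 1 (A1) models, at site and individual level, include county as five fixed indicators. Fixed effects are preferable to a random county intercept here: in simulation the random intercept gave type I error of 5.1% to 5.4%, and it would need its own degrees-of-freedom rule.

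Add a rurality indicator only if rurality was used as a stratum within county and varies there. If it is coded by county, it is aliased with the county indicators and must be left out.

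The cost is one sentence and 5 degrees of freedom: 34 to 29 with A1 alone, or 31 to 26 with all printed terms. If counties do not differ, the detectable difference rises by about 0.005 SD (A1 alone) to 0.01 SD (printed model), and power falls by 1 point or less.
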